2.11.9 Physical Examination Data

The physical examination data will be listed in the Appendix.

2.11.10 Concomitant Medications

Concomitant medications used during the study will be summarized in Post-text Table 14.3.23. Medications discontinued before the enrollment date will be

excluded from the summary. The World Health Organization (WHO) Drug Dictionary (WHO-DD, 01DEC2015 version) will be used to map the medication name to the Anatomical Therapeutic Chemical (ATC) classification codes for summary purpose.

If a medication is mapped to more than one ATC-code, a unique ATC-code will be selected based on the condition treated. The concomitant medications will be summarized by the medication category, medication class, and medication subgroup based on the ATC-codes. The medication category will be determined by the first character of the ATC-code. The medication class will be determined by the first three characters of the ATC-code. The medication subgroup will be determined by all the characters (maximum five characters) of the ATC-code.

2.12 Handling of Partial Dates and Partial Times

Complete date and time values were required for certain date fields on the CRFs (e.g., assessment date and time, dosing date and time, etc.). However, partial date values may have been acceptable for selected date fields on the CRFs (e.g., start dates of concomitant medications or adverse events prior to entry). In order to calculate the duration of events, the following assumptions were applied to estimate the complete date and time values for the partial event start date and time values:

- (1) If only the “time” value was missing, the first minute (00:01) of the day was used.
- (2) If only the “day” value was missing, the first day of the month was used.
- (3) If only the “month” value was missing, January was used.
- (4) If both “day” and “month” values were missing, January first was used.

The “year” value of the date field was required for all cases. The estimated event date/time should not be later than the available event stop date/time for a given event.

For those adverse events with partial AE stop date/time and stopped prior to the study termination, the following assumptions were applied to estimate the complete date values:

- (1) If only the “time” value was missing, the last minute (23:59) of the day was used.
- (2) If only the “day” value was missing, the last day of the month was used.
- (3) If only the “month” value was missing, December was used.
- (4) If both “day” and “month” values are missing, December 31st was used.

If the estimated AE stop date/time based on the assumptions listed above was later than the study termination date, the partial AE stop date/time was estimated from the study termination date/time.

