2.11.2 Adverse Events

Adverse events occurring while patients were on study medication during the treatment period or within 12 hours after the discontinuation of study medication will be summarized in Post-text Table 14.3.2. All incidences of AEs will be summarized in Post-text Table 14.3.3. The MedDRA[®] (Medical Dictionary for Regulatory Activities) V11.0 thesaurus will be used to map the AE verbatim to lowest level term (LLT), preferred term (PT) and System Organ Class (SOC) for summary purposes. Adverse event data including the AE verbatim term and the associated AE thesaurus preferred term will be provided in the patient data listings.

The most frequent AEs (e.g., those in at least 1% of all treated patients) will be summarized in Post-text Table 14.3.4.

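### Does the missing first-dose limit on imputed adverse-event starts in SAP 2.12 remove post-dose events from Table 14.3.2?

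*SAP*

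**What the plan says.** SAP 2.12 introduces its rules for partial start values by their use: "In order to calculate the duration of events, the following assumptions were applied to estimate the complete date and time values". It accepts partial values in selected fields only, and its examples are "start dates of concomitant medications or adverse events prior to entry".

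The start rules are:

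- only the time absent: "value was missing, the first minute (00:01) of the day was used";
- only the day absent: "value was missing, the first day of the month was used";
- only the month absent: "value was missing, January was used".

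One limit follows, at the upper end: "The estimated event date/time should not be later than the available event stop date/time for a given event". Adverse-event stops are imputed late instead of early, and they have a study boundary. The clause "If the estimated AE stop date/time based on the assumptions listed above was later than the study termination date" leads to the termination date and time being used instead. Starts have no matching boundary at first dose.

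SAP 2.11.2 assigns to Table 14.3.2 "Adverse events occurring while patients were on study medication during the treatment period or within 12 hours after the discontinuation of study medication". Table 14.3.3 takes every adverse event without a window. Protocol 9.6 names the same windowed summary as Table 14.3.2, and protocol 8.1.3 has adverse events entered on their CRF page from first dose until 12 hours after the last.

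**The concern.** The section guards one end of the study period and leaves the other open. An event that begins after dosing, on the dosing date, with no recorded time is given an onset before dosing. A missing day or month can move the onset back by days or weeks. Table 14.3.2 needs some comparison of event timing with dosing, and SAP 2.12 is the only rule the SAP gives for partial starts. A programmer might therefore carry the imputed start into that comparison.

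The event would then leave the on-treatment table and remain only in Table 14.3.3. The error at first dose would run one way, towards understating on-treatment adverse events of an opioid. SAP 2.11 does not say which set of events the later adverse-event tables use, so a loss could carry into those as well.

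**Working it through.** The plan states no figure on this point to reproduce. The check follows an affected record through the rule and then through the table.

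**1. What the rule does to the date.** The documents give no actual dose times, so assume a first dose on 14 March at 14:00.

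| Part missing | True onset | Imputed onset | Imputed onset precedes first dose by |
|---|---|---|---|
| Time | 14 March 16:00 | 14 March 00:01 | 14:00 − 00:01 = 13 h 59 min |
| Day | 15 March 09:00 | 1 March 09:00 | 13 d 5 h |
| Month | 15 March 09:00 | 15 January 09:00 | 58 d 5 h (59 d 5 h in a leap year) |

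For assumed first doses from 10:00 to 22:00, the first gap runs from 9 h 59 min to 21 h 59 min. Taking every minute of the day as a possible first-dose time, 1,438 of 1,440 fall after 00:01. So when an event on the dosing date has no time, misdating is close to certain. On any later date a start of 00:01 already follows the first dose, so the time rule matters on one calendar day only.

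**2. Where the imputed value goes.** The stated use is duration. With a true stop at 18:00, the imputed duration is 18:00 − 00:01 = 17 h 59 min against a true 2 h, an excess of 15 h 59 min. SAP 2.11.2 to 2.11.6 describe Tables 14.3.2 to 14.3.16 by incidence, seriousness, discontinuation, severity, relationship and subgroup. None reports duration, so this error reaches listings or derived data at most.

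**3. Whether the event leaves Table 14.3.2.** Let D be first dose, S the true onset, E the stop and S* the imputed start. A post-dose event has S ≥ D, and no event stops before it starts, so E ≥ S ≥ D.

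- *Overlap test* (was the event present on treatment?): S* < D ≤ E, so the interval contains the first dose and the event stays in. In the example, 00:01 < 14:00 < 18:00. An event still ongoing also overlaps. A partial stop is imputed late, or set to study termination, and neither precedes the first dose.
- *Onset-only test* (is S* ≥ D?): 00:01 is earlier than 14:00, so the event is dropped.

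Only the second test loses the event. The wording of SAP 2.11.2 and protocol 9.6 refers to events occurring on study drug and specifies no test on onset.

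**4. Size if an event were lost.** With the planned 315 treated patients (SAP 2.1), one patient whose only event of a term is lost changes that term's rate by 100 × 1/315 = 0.32 percentage points.

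**5. How often a record could qualify.** The documents do not show the CRF, so no count is possible. Patients are inpatients treated for at most 72 hours. Staff monitor them continuously for the first hour after first dose (protocol 6.1.3). CRF entry is due within 3 days of completion and query resolution within 5 days (protocol 10.1.4). A missing day or month for an event seen in hospital would be unusual.

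**The case for a change.** The best case for a change is this. The authors saw that imputation can cross a study boundary and closed only one end. The pre-entry examples are only examples, and adverse-event onset is not among the fields named as needing complete values. Treatment-emergent flags are often programmed on onset, so an onset-only test is a realistic choice. First- and last-dose times are already recorded from the Controller log (protocol 6.1.3), so a lower bound would cost a sentence or two and a few lines of code.

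Part of this stands. The SAP does not say whether onset or overlap decides entry to Table 14.3.2, nor whether imputed values play any part. That is missing detail, but it does not show that a result changes. Because protocol 8.1.3 starts adverse-event documentation at first dose, an analyst has grounds to treat an untimed event on that date as post-dose without imputing anything. That passage governs what is documented and sets no dating rule, so SAP 2.12 does not contradict it.

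A general floor at first dose would also bring faults. It would be wrong for the section's own examples, which begin before entry. In the missing-month case it would give 14 March 14:00, overriding the recorded day (15) and time (09:00). Serious events are captured for 30 days after the last dose (protocol 8.1.3.3), so a late one with a partial date could be counted as on-treatment.

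**Conclusion.** No change is needed. SAP 2.12 does lack a lower bound at first dose, and the misdating it allows is large for a single record: 13 h 59 min in the worked example. Used for its stated purpose, the rule affects only durations, which no planned adverse-event table reports. An event is lost from Table 14.3.2 only if three conditions hold together: a post-dose event with a partial onset that the rule moves to before first dose, use of the imputed start beyond duration, and entry decided by onset alone. The documents establish none of them, and the wording on events occurring under treatment points away from the third.

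The size would be 0.32 percentage points on a term's rate per affected patient, assuming 315 treated. The number of such patients is unknown and may be zero. Table 14.3.3 and the device dispense failure rate do not depend on this rule. The gap is one that an analyst can fill sensibly when writing the table specifications.

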2.13 The Presentation of Data Listing

In addition to the summary Tables presenting the summarized data, individual

patient response data for the efficacy analysis will be presented in Appendix 16.2. These by-patient data listings present the measurements that will be used in supporting the summary Tables. Other by-patient data listings of baseline characteristics and safety measurements will also be presented in Appendix 16.2.

2.14 Computer Software

All data analyses will be performed using SAS® for Windows, Release 9.1².

References

1. Johnson, N. L. and Kotz, S. (1970), Distributions in Statistics: Continuous Univariate Distributions — 1, New York: John Wiley & Sons.
2. SAS Release 9.1. SAS Institute Inc., Cary, North Carolina, 2004.

Table A-1 Evaluation Time Points with Evaluation Windows Used
 for the Summary of Global Assessment Data by Evaluation Time Point

Evaluation Time Point	Evaluation Time Point Number	Minutes from Baseline to Target Time	Evaluation Window (Minute)		
Baseline	0	1	-14	-	1
2 hours	1	121	2	-	181
4 hours	2	241	182	-	361
8 hours	3	481	362	-	721
16 hours	4	961	722	-	1201
24 hours	5	1441	1202	-	1681
32 hours	6	1921	1682	-	2161
40 hours	7	2401	2162	-	2641
48 hours	8	2881	2642	-	3121
56 hours	9	3361	3122	-	3601
64 hours	10	3841	3602	-	4081
72 hours	11	4321	4082	-	4561
80 hours	12	4801	4562	-	5041
Interim	x.x			---	

Note: Unscheduled evaluation time points and time points for premature termination are considered as regularly scheduled time points. The time point closest to the target time will be used to determine the evaluation time-specific measurement. If there are two measures that obtained at the same time distance away from the target time for the same evaluation time point number, the one prior to the target time will be used in the summary. Measures that do not fall within the evaluation windows will be considered as interim data and assigned a decimal evaluation time point number between two evaluation time point numbers in integers (e.g., 2.1 or 3.9).

Table A-2 Scheduled Evaluation Time Points with Evaluation Windows Used for the Summary of Pain Assessment Data, Blood Pressures, and Heart Rates by Evaluation Time Point

Evaluation Time Point	Evaluation Time Point Number	Minutes from Baseline to Target Time	Evaluation Window (Minute)		
Screening	-1	-15	≤ -15		
Baseline	0	1	-14	-	1
15 minutes	1	16	2	-	23
30 minutes	2	31	24	-	38
45 minutes	3	46	39	-	53
1 hour	4	61	54	-	91
2 hours	5	121	92	-	181
4 hours	6	241	182	-	301
6 hours	7	361	302	-	421
8 hours	8	481	422	-	541
10 hours	9	601	542	-	661
12 hours	10	721	662	-	841
16 hours	11	961	842	-	1081
20 hours	12	1201	1082	-	1321
24 hours	13	1441	1322	-	1561
28 hours	14	1681	1562	-	1801
32 hours	15	1921	1802	-	2041
36 hours	16	2161	2042	-	2281
40 hours	17	2401	2282	-	2521
44 hours	18	2641	2522	-	2761
48 hours	19	2881	2762	-	3001
52 hours	20	3121	3002	-	3241
56 hours	21	3361	3242	-	3481
60 hours	22	3601	3482	-	3721
64 hours	23	3841	3722	-	3961

Protocol No. IAP312: FINAL REPORT
Statistical Analysis Plan

68 hours	24	4081	3962	-	4201
72 hours	25	4321	4202	-	4441
76 hours	26	4561	4442	-	4681
Interim	x.x			---	

Note: Unscheduled evaluation time points and time points for premature termination are considered as regularly scheduled time points. The time point closest to the target time will be used to determine the evaluation time-specific measurement. If there are two measures that obtained at the same time distance away from the target time for the same evaluation time point number, the one prior to the target time will be used in the summary. Measures that do not fall within the evaluation windows will be considered as interim data and assigned a decimal evaluation time point number between two evaluation time point numbers in integers (e.g., 2.1 or 3.9).

Table A-3 Scheduled Evaluation Time Points with Evaluation Windows Used for the Summary of Respiratory Rates and Oxygen Saturation Data by Evaluation Time Point

Evaluation Time Point	Evaluation Time Point Number	Minutes from Baseline to Target Time	Evaluation Window (Minute)		
Screening	-1	-15	≤ -15		
Baseline	0	1	-14	-	1
15 minutes	1	16	2	-	23
30 minutes	2	31	24	-	38
45 minutes	3	46	39	-	53
1 hour	4	61	54	-	76
1.5 hours	5	91	77	-	106
2 hours	6	121	107	-	136
2.5 hours	7	151	137	-	166
3 hours	8	181	167	-	196
3.5 hours	9	211	197	-	226
4 hours	10	241	227	-	256
4.5 hours	11	271	257	-	286
5 hours	12	301	287	-	316
5.5 hours	13	331	317	-	346
6 hours	14	361	347	-	376
6.5 hours	15	391	377	-	406
7 hours	16	421	407	-	436
7.5 hours	17	451	437	-	466
8 hours	18	481	467	-	496
8.5 hours	19	511	497	-	526
9 hours	20	541	527	-	556
9.5 hours	21	571	557	-	586
10 hours	22	601	587	-	616
10.5 hours	23	631	617	-	646

Protocol No. IAP312: FINAL REPORT
 Statistical Analysis Plan

11 hours	24	661	647	-	676
11.5 hours	25	691	677	-	706
12 hours	26	721	707	-	736
12.5 hours	27	751	737	-	766
13 hours	28	781	767	-	796
13.5 hours	29	811	797	-	826
14 hours	30	841	827	-	856
14.5 hours	31	871	857	-	886
15 hours	32	901	887	-	916
15.5 hours	33	931	917	-	946
16 hours	34	961	947	-	976
16.5 hours	35	991	977	-	1006
17 hours	36	1021	1007	-	1036
17.5 hours	37	1051	1037	-	1066
18 hours	38	1081	1067	-	1096
18.5 hours	39	1111	1097	-	1126
19 hours	40	1141	1127	-	1156
19.5 hours	41	1171	1157	-	1186
20 hours	42	1201	1187	-	1216
20.5 hours	43	1231	1217	-	1246
21 hours	44	1261	1247	-	1276
21.5 hours	45	1291	1277	-	1306
22 hours	46	1321	1307	-	1336
22.5 hours	47	1351	1337	-	1366
23 hours	48	1381	1367	-	1396
23.5 hours	49	1411	1397	-	1426
24 hours	50	1441	1427	-	1501
26 hours	51	1561	1502	-	1621
28 hours	52	1681	1622	-	1741
30 hours	53	1801	1742	-	1861

Protocol No. IAP312: FINAL REPORT
 Statistical Analysis Plan

32 hours	54	1921	1862	-	1981
34 hours	55	2041	1982	-	2101
36 hours	56	2161	2102	-	2221
38 hours	57	2281	2222	-	2341
40 hours	58	2401	2342	-	2461
42 hours	59	2521	2462	-	2581
44 hours	60	2641	2582	-	2701
46 hours	61	2761	2702	-	2821
48 hours	62	2881	2822	-	2941
50 hours	63	3001	2942	-	3061
52 hours	64	3121	3062	-	3181
54 hours	65	3241	3182	-	3301
56 hours	66	3361	3302	-	3421
58 hours	67	3481	3422	-	3541
60 hours	68	3601	3542	-	3661
62 hours	69	3721	3662	-	3781
64 hours	70	3841	3782	-	3901
66 hours	71	3961	3902	-	4021
68 hours	72	4081	4022	-	4141
70 hours	73	4201	4142	-	4261
72 hours	74	4321	4262	-	4441
76 hours	75	4561	4442	-	4681
Interim	x.x			---	

Note: Unscheduled evaluation time points and time points for premature termination are considered as regularly scheduled time points. The time point closest to the target time will be used to determine the evaluation time-specific measurement. If there are two measures that obtained at the same time distance away from the target time for the same evaluation time point number, the one prior to the target time will be used in the summary. Measures that do not fall within the evaluation windows will be considered as interim data and assigned a decimal evaluation time point number between two evaluation time point numbers in integers (e.g., 2.1 or 3.9).
